Glucose management of patients in the treatment group will be guided by readings from the Dexcom G6. The Dexcom device will provide interstitial fluid glucose measurements at five-minute intervals used to construct a graph for trending CGM levels as well as an approximate rate of change. Threshold alarm for hypoglycemia will be set with CGM glucose values < 100 mg/dL and system alarm for CGM glucose value < 55 mg/dL. The alarms will be incorporated into the decision protocol for treatment of low blood glucose levels to achieve the stated goal of improved glycemic control and decreased rates of hypoglycemia within the hospital setting.

This requires a detailed protocol of how the devices is to be used in the RCT and that all clinical staff assigned to the patient be trained to follow the protocol (i.e., staff must be trained to use CGM as a patient care tool).

The Dexcom G6 protocol includes the following:

- 1) The treatment group will have the data displayed with alarms set for glucose measurements of
 - A. Threshold alarm CGM glucose < 100 mg/dL
 - B. The urgent low soon alert, indicated by 2 downward arrows on the device reading. (Blood sugar of 55 mg/dL in less than 20 minutes)
 - C. Urgent low system alarm set at CGM glucose < 55 mg/dL.
- 2) Definition of target range is CGM glucose 100 -180 mg/dL
- 3) Definition of hypoglycemia is CGM glucose < 70 mg/dL (2 consecutive CGM readings below threshold)
- 4) Definition of hyperglycemia is CGM glucose > 300 mg/dL (2 consecutive CGM readings above threshold)
- 5) Definition of Severe hypoglycemia (see below)

Severe Hypoglycemia: the event required assistance of another person due to altered consciousness, and required another person to actively administer carbohydrate, glucagon, or other resuscitative actions. This means that the subject was impaired cognitively to the point that he/she was unable to treat himself/herself, was unable to verbalize his/her needs, was incoherent, disoriented, and/or combative, or experienced seizure or coma. These episodes may be associated with sufficient neuroglycopenia to induce seizure or coma. If plasma glucose measurements are not available during such an event, neurological recovery attributable to the restoration of plasma glucose to normal is considered sufficient evidence that the event was induced by a low plasma glucose concentration.

Definition of severe hyperglycemia/DKA:

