Hyperglycemic events are classified as severe hyperglycemia or DKA if the following are present:

- Symptoms such as polyuria, polydipsia, nausea, or vomiting;
- Serum ketones $> 1.0 \text{ mmol/L}$ or large/moderate urine ketones;
- Either arterial blood pH < 7.30 or venous pH < 7.24 or serum bicarbonate < 15 ; and treatment provided in a health care facility

Research Blood Glucose Protocol will be followed at all times.

Research Blood Glucose Protocol:

i. If CGM $> 180 \text{ mg/dL}$, patient will receive usual care based on attending physician or advanced practice professional orders based on readings from AC and HS finger stick blood glucose readings. In other words, CGM readings will not be used for management of glucose levels $> 180 \text{ mg/dL}$. Physicians and Advanced Practice Professionals (APPs – includes nurse practitioners or physician assistants) will be educated on the fact that, to prevent the risk of insulin stacking, CGM glucose values should not be used to bolus insulin or dose insulin. Elevated CGM readings $> 180 \text{ mg/dL}$ should not be relayed to on-call physicians or APPs by nursing staff. Pharmacy personnel will also be educated to not use CGM readings for dosing of insulin in order to prevent insulin stacking.

ii. If CGM 100-180 mg/dL with arrow direction  : continue usual care

iii. If CGM 100-180 mg/dL with arrow direction  : Recheck CGM in 1 hour; continue usual care

iv. If CGM 100-180 mg/dL with arrow direction  : Recheck CGM in 30 min; continue usual care

v. If CGM 100-180 mg/dL with arrow direction  (double arrow down): Recheck CGM in 15 min; continue usual care

vi. If CGM between 70-100 mg/dL and arrow direction  or  : continue usual care

vii. If CGM between 70-100 mg/dL and arrow direction  (horizontal) Recheck CGM in 30 min and follow research blood glucose protocol

viii. If CGM between 70-100 mg/dL and arrow  : Recheck CGM in 15 min and follow research blood glucose protocol

ix. If CGM between 70-100 mg/dL and arrow direction  (1 arrow down) Administer one of the following options and recheck CGM device 15 minutes after intervention and follow research blood glucose protocol again:

1. 2 oz. (60 ml) juice
2. 2 glucose tablets
3. 1/2 tube glucose gel

4. 12.5 ml D50W IV

x. If CGM between 70-100 mg/dL and arrow direction  (2 arrows down)

Administer one of the following options and recheck CGM device 15 minutes after intervention and follow research blood glucose protocol again:

1. 4 oz. (120 ml) juice

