2. 4 glucose tablets
3. 1 tube glucose gel
4. 25 ml D50W IV

xi. If CGM < 70 mg/dL: confirm with finger stick blood glucose and initiate standard of care per hospital hypoglycemia protocol per hospital policy. Resume CGM study research blood glucose protocol after two hours.

Additional standing orders in the Dexcom G6 protocol:

- a. Protocol will not encompass changes in basal, pre-meal, or corrective factor insulin ordered by the attending physician.
- b. Provide 24-hour CGM printout of glucose monitoring on morning rounds to the physicians caring for patients in the treatment group for their consideration in adjusting the scheduled basal/bolus insulin based on the CGM pattern. Information will also be provided regarding any interventions that were provided to the patient as a result of the research glucose protocol during the prior 24 hours.
- c. Review 24-hour CGM printout with patient in the treatment group to outline the effect of food, insulin and any exercise that may have occurred during the past 24 hours on glycemic control.

Usual Care for Glucose Control (Control Group): Patients assigned to the control group and wearing the Dexcom G6 PRO, will receive usual care as ordered by their attending physician. That means, the patient's glucose management will be based on reading from the blood glucose test that are conducted within a 24-hour period, and orders for glucose management will be determined by the attending physician.

Outcome Measures: Impact of CGM on key patient health indicators will be tracked during the enrolled patient's inpatient stay for up to 10 days. Number of events or amount of time will be calculated in consideration by the total time while the patient is hospitalized with an active Dexcom device (i.e., total time in which the Dexcom device is in use will serve as the denominator). Patients with less than 48 hours of Dexcom device reading will be excluded from outcome data analyses. Key outcomes abstracted from the Dexcom device will include:

- 1) Episodes of hypoglycemia (two consecutive CGM reading above or below threshold)
- 2) Episodes of hyperglycemia (two consecutive CGM reading above or below threshold)
- 3) Episodes of severe hypoglycemia
- 4) Episodes of severe hyperglycemia/DKA
- 5) Total time spent in the target range of 100-180
- 6) Number of times that CGM readings would change management of hypoglycemia compared to standard care

Other outcome measures to be collected include:

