Data Retention and/or Data Destruction Plan: All paper data related to the study will be stored securely in a locked file cabinet in a secured room. Any digital data files will be stored in a password protected BSWH maintained network. Access to data will be restricted to listed key study personnel only. Data abstracted for this study will be retained for study recordkeeping purposes and research compliance until the completion of the study. Once the study is closed, research related documents will be stored at the Dallas research Storage facility for an indefinite amount of time.

Subject Withdrawal:

Subjects may choose to withdraw from the study at any time prior to the conclusion of the study. Patients with less 48 hours of Dexcom device readings will be excluded from outcome data analyses.

Reporting adverse events or other significant events: Adverse events will be reported to the IRB accordingly and promptly.

Data collection:

Data will be collected for evaluation purposes and reported only in aggregate. Dexcom data will be compared to historical quality data reports of hypoglycemic events and hyperglycemic events on glucose management. Below is a list of variables that will be collected:

Table 1: Data Collection Variables	
Variable	Source
Demographics	
MRN	EPIC
Name (first, last)	EPIC
DOB	EPIC
Gender	EPIC
Race	EPIC
Ethnicity	EPIC
Clinical Outcomes	
Admitting Diagnosis	EPIC
Most recent hemoglobin A1C	EPIC
Length of Stay	EPIC
Episodes of hypoglycemic events	Dexcom
Episodes of hyperglycemic events	Dexcom
Total time spent in the target range of 100-180	Dexcom

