Outcome Measures: Impact of CGM on key patient health indicators will be tracked during the enrolled patient's inpatient stay for up to 14 days. Number of events or amount of time will be calculated in consideration by the total time while the patient is hospitalized with an active Dexcom Gen6 device (i.e., total time in which the Dexcom Gen6 is in use will serve at the denominator). Patients with less than 48 hours of Dexcom Gen6 reading will be excluded from outcome data analyses. Key outcomes abstracted from the Dexcom Gen6 will include:

- 1) Episodes of hypoglycemia (two consecutive CGM reading above or below threshold)
- 2) Episodes of hyperglycemia (two consecutive CGM reading above or below threshold)
- 3) Episodes of severe hypoglycemia
- 4) Episodes of severe hyperglycemia/DKA
- 5) Total time spent in the target range of 100-180
- 6) Number of times that CGM readings would change management of hypoglycemia compared to standard care

Other outcome measures to be collected include:

- 1) Questionnaires regarding perceptions of use of CGM devices in the inpatient setting to be completed by nurses and physicians
- 2) Questionnaires about the anticipated experience and actual experience of wearing a CGM device by the patient. To be administrated by research nurse immediately prior to application of the device and immediately after removal of the final device applied (i.e., immediately prior to discharge)
- 3) Length of stay
- 4) The Diabetes Treatment satisfaction questionnaire-change (DTSQc) at completion of Dexcom Gen data collection (11)

Other variables to be collected and entered in the data analyses include:

- 1) Patient demographics
- 2) Medical history
- 3) Admitting diagnosis
- 4) Information about home diabetic regimen
- 5) Most recent hemoglobin A1c found in EHR
- 6) Length of time since diagnosis of diabetes
- 7) Any skin irritation at the site of monitor device insertion

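### Severe hypoglycemia and severe hyperglycemia/DKA are listed as device-abstracted outcomes, but their definitions rest on clinical and laboratory findings that the sensor does not record, and no other outcome source is named

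*Protocol*

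**What the plan says.** The Outcome Measures section of the Protocol opens its list of six with "Key outcomes abstracted from the Dexcom device will include". The third item is "Episodes of severe hypoglycemia" and the fourth is "Episodes of severe hyperglycemia/DKA". The combined protocol and SAP has the same list under "Key outcomes abstracted from the Dexcom Gen6 will include".

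The section on CGM-informed care in the Protocol states what the device produces: "The Dexcom device will provide interstitial fluid glucose measurements at five-minute intervals", from which a trend graph and an approximate rate of change are built.

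The definitions come shortly afterwards. Severe hypoglycemia means that "the event required assistance of another person due to altered consciousness" and that another person had to give treatment actively. If no plasma glucose is available, neurological recovery once glucose is restored is enough evidence. Severe hyperglycemia/DKA needs symptoms, raised serum or urine ketones, and an acid-base criterion ("Either arterial blood pH < 7.30 or venous pH < 7.24", or low bicarbonate) with treatment in a health care facility. The combined document gives the same definitions.

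Table 1 in both documents has a Dexcom-sourced row for hypoglycemic events, one for "Episodes of hyperglycemic events" and one for time in range. It has no row for either severe outcome, or for ketones, pH or bicarbonate.

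**The concern.** The plan names a source for these two outcomes, and that source cannot produce them. An analyst who follows the text would search the device download, find nothing that meets either definition, and could report no severe events in either arm. That result would describe the data source and not the patients.

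The Anticipated Benefits section lists fewer severe hypoglycemic and fewer severe hyperglycemic events as expected gains in the treatment group. Those expectations cannot be examined from the source given. If the gap is filled informally at the end of the study, nothing in the plan ensures that both arms are searched in the same way or over the same period.

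**Working it through.** No arithmetic is needed to establish the mismatch. The check sets each defining element beside what the device is said to record: interstitial glucose every five minutes, its trend and its approximate rate of change.

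| Outcome | Defining element | Shown by the sensor? |
|---|---|---|
| Severe hypoglycemia | Altered consciousness needing another person's help | No |
| Severe hypoglycemia | Active treatment given by another person | No |
| Severe hypoglycemia | Neurological recovery (when no plasma glucose is available) | No |
| Severe hyperglycemia/DKA | Symptoms | No |
| Severe hyperglycemia/DKA | Serum or urine ketones | No |
| Severe hyperglycemia/DKA | pH or bicarbonate, with treatment in a facility | No |

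None of the elements can be observed in the trace. The severe hypoglycemia definition contains no CGM threshold. For DKA the trace can show the accompanying glucose excursion, but none of the three listed criteria. A severe event may coincide with a CGM episode below 70 or above 300 mg/dL and be counted under item 1 or 2. The trace alone cannot classify it as severe.

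**Other possible sources.** Table 1 names none. The Reportable Adverse Events section makes both events reportable by these definitions, in both arms. It is written for reporting to the IRB, and neither document connects it to outcomes 3 and 4.

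**Could detection differ by arm?** The two outcomes need separate answers.

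- *Severe hypoglycemia: possible.* Treatment-arm staff have three low-glucose alerts (below 100 mg/dL, urgent low soon, below 55 mg/dL) and confirm CGM values below 70 mg/dL by finger stick. Control-arm staff cannot see the readings, and usual care is described as four glucose checks per 24 hours.
- *DKA: not through the alarms.* There is no high-glucose alarm, CGM values above 180 mg/dL are not used for management, and nursing staff are told not to relay them to on-call clinicians. Treatment-arm physicians do receive a 24-hour CGM printout each morning. The documents do not say that it prompts ketone or acid-base testing.

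**What changes once the source is clinical.** Two device-based rules in Outcome Measures then fit poorly:

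- The denominator is time with the device in use. A clinical event can occur while the device is off, for example around an MRI, when replacement is allowed up to twelve hours after return to the room.
- Patients with less than 48 hours of readings are excluded from outcome analyses. One DKA event is a criterion for discontinuation, so a patient discontinued for DKA before 48 hours of readings would be removed from the analysis of that same outcome.

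**The case against.** The strongest reply is that these events are already captured. The principal investigator must report all serious adverse events. Anticipated adverse events are tracked, severe hypoglycemia and DKA are explicitly reportable, and both appear among the grounds for discontinuation. A withdrawal other than withdrawal of consent goes to the IRB within 3 days. Table 1 is also not exhaustive: medical history and skin irritation are to be collected and have no row in it, so absence from the table proves little. On this view only a linking sentence is missing.

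Much of this stands. A reader might infer that severe events would go unrecorded, and the documents do not support that. What remains is that the plan states a source, the source is wrong, and the adverse event route is not named as the replacement. Table 1 is supporting evidence only; the heading over the outcome list is what creates the contradiction.

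A reader might also infer that alarms bias detection of both outcomes. For DKA they cannot, for the reasons above. For severe hypoglycemia the bias is a possibility and not an established fact: an event with altered consciousness and active rescue should usually be evident on a ward with or without an alarm.

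**Conclusion.** The point holds as a contradiction between stated source and definition, present in both documents and affecting two of the six key outcomes. It rests on the definitions as written and on the documents' own account of what the device records. No assumed figure is involved.

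Its reach is limited in two ways.

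- **The primary comparison is intact.** Data Analysis first says that the glucose-management indicators will serve as primary outcomes, which might suggest that the severe events are included. The next sentence names CGM hypoglycemic events and time in range as the measures to be tested, and both are sensor-derived.
- **It cannot be said that one missed event would decide a safety comparison.** The documents give no severe-event rate and specify no test for these outcomes. If 40 patients split 20 and 20 and there is one event in total, it falls in either arm with probability 20/40 = 0.5. The two-sided Fisher p-value is then 0.5 + 0.5 = 1.0, so a single event settles nothing inferentially. It would still alter the descriptive count, which is why ascertainment should be the same in both arms.

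This should be corrected before outcome data are abstracted.

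**What to change.** - Move outcomes 3 and 4 out of the device-abstracted list. Items 1, 2 and 5 (CGM episodes and time in range) stay there.
- State that outcomes 3 and 4 are ascertained from the EHR (clinical notes, treatment records, laboratory ketones, pH and bicarbonate) and from the adverse event log, using the existing definitions and one abstraction procedure for both arms.
- Add rows for both outcomes to Table 1, with EPIC and the adverse event log as source.
- Report both for all randomized patients over the in-hospital study period. Do not limit them to device-on time or to patients with at least 48 hours of readings, so that a patient discontinued early for DKA is still counted.

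The definitions and clinical procedures do not change. The cost is protocol wording, a few table rows and a small amount of extra chart abstraction for 40 inpatients whose EPIC records are already being abstracted.

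### Severe hypoglycemia and severe hyperglycemia/DKA are sourced from a sensor that cannot identify them and fall under the 48-hour exclusion, so their count by arm may be incomplete

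*Protocol*

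**What the plan says.** Protocol, Outcome Measures, puts six key outcomes under one lead-in: "Key outcomes abstracted from the Dexcom device will include". The third is severe hypoglycemia and the fourth is "Episodes of severe hyperglycemia/DKA". Tracking covers the "inpatient stay for up to 10 days", but for event counts and times the "total time in which the Dexcom device is in use will serve as the denominator". The section adds: "Patients with less than 48 hours of Dexcom device reading will be excluded from outcome data analyses". Subject Withdrawal repeats it: "Patients with less 48 hours of Dexcom device readings will be excluded from outcome data analyses". Neither place makes an exception.

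The two severe events are defined in the section on CGM-informed care. A severe low is a clinical state in which consciousness is altered and someone else has to treat the patient. No CGM threshold appears, and neurological recovery can stand in for a missing plasma glucose. Severe hyperglycemia/DKA needs symptoms, ketones, a pH or bicarbonate criterion, and treatment in a care facility.

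Table 1 has a row for "Episodes of hypoglycemic events" and one for the hyperglycemic counterpart, both with Dexcom as source. It has no row for either severe event.

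Criteria for Discontinuation of Individual Participants allows a stop for a severe low with seizure or loss of consciousness or for DKA (item 2, at the investigator's discretion), for one DKA or HHNS episode (item 4), and for ICU transfer or deterioration (item 6). Reportable Adverse Events covers both severe lows and DKA.

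The Combined protocol and SAP has the same outcome list and 48-hour rule, with tracking for up to 14 days.

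**The concern.** Two of the six key outcomes are assigned to a data source that does not hold the information needed to classify them. The analysis population for those outcomes is then set by hours of sensor data, although the events can be known without a sensor. Because some of these events are also grounds for a stop, the event itself could be the reason a patient has too few readings. Inclusion would then depend on the outcome.

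Anticipated Benefits in the Protocol names fewer severe hypoglycemic and fewer severe hyperglycemic events in the treatment group. A reader of the results would look to the count by arm to see whether that was borne out. If the written source and exclusion rule are followed literally, that count could omit a patient because of the event.

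**Working it through.** The documents state no severe-event rate, stop rate or power figure, so there is no figure of theirs to reproduce. The check is mainly a comparison of text, with arithmetic for illustration.

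**1. Source against definition**

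| Item | What it needs | What the sensor gives |
|---|---|---|
| Severe hypoglycemia | Mental state; active treatment by another person | Interstitial glucose every five minutes, trend, approximate rate of change |
| Severe hyperglycemia/DKA | Symptoms, ketones, pH or bicarbonate, treatment | The same |

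The sensor file cannot classify either event. This holds whatever the event rate.

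**2. How an event could be excluded.** All of these must happen:
- a severe event occurs early in wear;
- it meets a discontinuation criterion, which for a severe low under item 2 means seizure or loss of consciousness;
- the stop is made, and it ends recording and not only study treatment;
- fewer than 48 hours of readings have accrued.

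The documents do not say that the sensor comes off at a stop. For a CGM value below 70 mg/dL, item xi of the Research Blood Glucose Protocol points to continuation: "Resume CGM study research blood glucose protocol after two hours". So the loss is possible, not automatic. Whether an event after sensor removal counts is also unclear, because the denominator is device time while the tracking window is the stay.

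**3. Length of the exposed window.** Readings come every five minutes, so 48 hours is 48 × 60 / 5 = 576 readings. The Protocol mentions a 2-hour warm-up under Anticipated Challenges. Assuming no readings are stored then, 48 + 2 = 50 hours of wear are needed at minimum. The inclusion criteria ask for an expected stay of 2 or more days, so this window may be much of a short stay.

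**4. Effect on a count.** Forty patients at 1:1 give 20 per arm if allocation comes out even. Suppose one arm has one severe event and that patient is excluded.
- Before: 1/20 = 5.0%. Exact 95% limits: lower 1 − 0.975^(1/20) = 0.1%; upper solves (1 − p)^20 + 20p(1 − p)^19 = 0.025, giving 24.9%.
- After: 0/19 = 0%. Upper limit 1 − 0.025^(1/19) = 17.6%.

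**5. Effect on a test.** With k events in one arm of 20 and none in the other, the two-sided Fisher p is 2 × C(20,k) / C(40,k).
- k = 1: 2 × 20/40 = 1.0
- k = 2: 2 × 190/780 = 0.49
- k = 4: 2 × 4,845/91,390 = 0.11

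None is conclusive, so the cost is in the descriptive count.

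**6. How likely is one loss?** This rests wholly on an assumed per-patient risk p that a severe event ends recording before 48 hours of readings. The chance of at least one such loss is 1 − (1 − p)^n.

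| Assumed p | n = 20 | n = 40 |
|---|---|---|
| 1% | 18% | 33% |
| 2% | 33% | 55% |
| 5% | 64% | 87% |

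These are not estimates. They show only that the answer depends on a rate the documents do not supply.

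**The case against.** The strongest reply is that nothing is lost. The Protocol requires all SAEs to be reported, lists severe hypoglycemia and DKA as reportable, and tracks anticipated adverse events for frequency, with no minimum wear time. The 48-hour rule covers outcome analyses only. A reader might infer that the plan leaves severe events unrecorded or makes the safety count wrong; the documents do not support that. This part of the reply stands. What it leaves open is that no text makes those records the source for key outcomes 3 and 4, exempts them from the 48-hour rule, or plans a comparison by arm.

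A second reply is that the lead-in to the outcome list is loose and Table 1 is not exhaustive: medical history and skin irritation are to be collected and have no row either. That is fair, and the missing rows alone would prove little. The mismatch between the stated source and the definitions does not depend on Table 1.

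Third, exclusion needs a chain of events, and the eligibility criteria remove ICU patients and those who may need IV insulin, which plausibly lowers the risk. This stands too. A reader might infer that every early severe event is dropped, or that one arm is favoured. The stop is permissive and partly discretionary, the criteria apply to both arms, and no rates are given, so neither inference is supported.

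Fourth, the hypotheses concern sensor-measured episodes, and Data Analysis names the t-test only for hypoglycemic events and time in range. A reader might think a primary result is threatened. It is not on this point: those two outcomes do come from the sensor, and requiring enough sensor data for them is a separate question.

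**Conclusion.** The point holds in a limited form. The mismatch of source is plain from the text and needs no assumption: two of six key outcomes are assigned to a device that cannot classify them. The exclusion is a conditional risk. It arises only if a severe event leads to a stop that ends recording before 48 hours of readings, which takes at least 50 hours of wear if the warm-up stores none.

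The consequence is a possibly incomplete count by arm for two descriptive outcomes in a 40-patient pilot. The illustrative size is one event in an arm of 20, 5.0% becoming 0%, with no test conclusive either way. Few or no patients may be affected. The correction is still worth making, because an analysis population for severe events should not depend on the events themselves, and the records needed for the repair are already required.

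**What to change.** Leave the discontinuation criteria as they are. No sensor needs to stay on after a stop. In the Protocol's Outcome Measures section and Table 1, with Subject Withdrawal brought into line:

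- Take outcomes 3 and 4 out of the Dexcom-abstracted list and add a Table 1 row for each, naming EPIC and the reportable-event records as the source.
- Apply the 48-hour rule only to sensor-derived outcomes.
- Report severe events by randomised arm in all randomised patients over the inpatient stay up to 10 days, including after a stop unless consent is withdrawn. Give both the number of patients with at least one event out of all randomised and the events per patient-day in hospital. The second replaces device time, which no longer fits once events without a sensor are counted, and it allows for differing lengths of stay.
- Report stops by arm and by criterion.

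The cost is a few sentences, two table rows and minor chart abstraction in 40 patients, much of it overlapping with reporting already required. The drawback is that some time after a stop will reflect usual care and not the assigned strategy, which the report should state.
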